10.7.5 Physical Examination, ECGs, and Other Observations Related to Safety

10.7.5.1 Physical Examination

Full physical examination at Screening and EOT will be summarized.

A listing of physical examination findings during the study will be presented, including an indication of abnormal and clinically significant findings as entered on the Physical Examination CRFs.

10.7.5.2 Electrocardiograms

The mean QTcF (msec) from ECGs performed in triplicate periodically over the study period will be summarized at scheduled time points/visits. Change in QTcF from baseline at all scheduled post-baseline time points/visits will also be summarized.

A listing of QTcF over time will also be presented, including an indicator of clinically significant assessments as indicated on the ECG 1 and ECG 2 CRFs.

Baseline is defined as the last measurement prior to first study drug administration. If the assessment is made on the same day as first study drug administration and there are no times to indicate that it was after administration, it will be assumed to be prior and therefore qualify as the baseline measurement.

The number and percentage of patients with ECG abnormalities will be presented. Abnormality criteria to be used in the determination of ECG abnormalities are defined as follows.

Parameter	Abnormality Criteria
	Maximum value at any post visit baseline visit:
	≥ 450 - < 480 msec,
	≥ 480 - < 500 msec and
QTcF (msec)	≥ 500 msec
	Maximum change from baseline:
	\geq 30 to < 60 msec and
	≥ 60 msec

All ECG parameter values will be listed for patients meeting any abnormality criteria. A subject data listing will be provided that identifies patients with abnormal findings as assessed by the investigator/cardiologist after the first dose of study treatment for each type of ECG abnormality.

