	• Phenotype and markers of immune cells (ICs) activation in peripheral blood (eg, CD3, CD8, CD4, regulatory T cells (T Regs ), CD4 memory cells, CD25, FOXP3, CD45RA, ICOS, CD14, CD45, CD56, CD19 and inducible T-cell Costimulator Ligand (ICOSLG) fluorescence-activated cell sorting (FACS) or ChipCytometry)	

	• PBMCs gene signature (RNA) (transcriptomics/Nanostring)
	• ICOS Receptor Occupancy (RO) in PBMCs (KY1044 as single agent in Phase 1 only)
Statistical analysis:	Primary endpoints: Phase 1
	Treatment-related AEs/SAEs coded by primary System Organ Class (SOC) and Preferred Term (PT) will be summarized in those receiving at least one infusion of KY1044. Additional summaries by severity of AEs/SAEs will also be produced.
	Actual and change from baseline data for vital signs, ECG parameters and clinical laboratory values will be reported using summary statistics.
	The number of dose interruption, reductions and incidence of DLTs will be summarized.
	Primary endpoint: Phase 2
	ORR per RECIST 1.1 will be presented for each indication along with exact 80% and 95% confidence intervals
	Phase 1 will be reported by dose group(s) within KY1044 single agent and KY1044 combination groups.
	Phase 2 of the study will be reported by indication and dose group(s) within KY1044 single agent and KY1044 combination groups, split by anti-PD-(L)1 naïve and pre-treated groups.
	Wherever possible, patients with the same tumor type who have received the recommended dose(s)/schedule(s) of KY1044 as single agent or in combination will be pooled for analysis.
	No formal statistical testing will be performed during Phase 2. Instead confidence intervals will be constructed around the objective response rate observed in each cohort, and this will enable decisions to be made around the likely success of future studies. A Go-no-go decision grid for Phase 2 cohort expansion will be developed for each indication
	Final data analysis will be performed at the end of the study.
Planned study dates:	Q1 2019
Start of clinical phase	Q3 2023 / Q1 2024
End of clinical phase	
Duration of the study:	The duration of the study for each patient will consist of up to 28 days of screening, up to 48 months of treatment (approximately 70 cycles) and 90 days of safety follow-up.

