# 2.2 Endpoints

# 2.2.1 Primary Endpoints

# Phase 1

- Safety: Incidence and severity of AEs and SAEs, including changes in laboratory parameters, vital signs and electrocardiograms (ECGs)
- Tolerability: Dose interruptions, reductions and dose intensity
- The incidence of DLTs with KY1044 as single agent during the first 21 days of treatment
- The incidence of DLTs with KY1044 in combination with atezolizumab during the first 21 days of treatment

# Phase 2

• ORR per Response Evaluation Criteria in Solid Tumors Version 1.1 (RECIST 1.1)

10-Nov-2021 Version number: 1

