1	Abnormal cardiac biomarker testing, including abnormal ECG	
 
Recommend baseline ECG and cardiac biomarker assessment (BNP, troponin) to establish if there is a notable change during therapy
 
Mild abnormalities should be observed closely during therapy
 
	√ if abnormal
2	Abnormal screening tests with mild symptoms	
 
Control cardiac diseases (eg, heart failure, atrial fibrillation) optimally
 
Control cardiac disease risk factors proactively (including hypertension, hyperlipidemia, discontinue smoking, and monitor diabetes)
 
	$\checkmark$
3	Moderately abnormal testing or symptoms with mild activity	
 
BNP >500 pg/mL, troponin >99% institutional normal, new ECG findings (QTc prolongation, new conduction disease, or ST-T wave changes)
 
Consider withholding ICI 
 
If a period of stabilization is achieved and definite cardiac toxicity was not identified, it may be reasonable to consider re-challenging the patient with ICI, with heightened monitoring.
 
 
 
If confirmed cardiac injury or decompensation, hold ICI therapy until stabilized.
 
Optimally treat identified cardiac conditions
 
Consider corticosteroids if myocarditis suspected (Note 2)
 
	$\checkmark$
4	Moderate to severe decompensation, intravenous medication or intervention required, life threatening conditions	
 
Permanently discontinue ICI
 
If myocarditis is identified, consider high-dose corticosteroids (1 mg/kg methylprednisolone (IV) for at least several days) until improved to Grade ≤1, after that consider at least 4–5 weeks of tapering doses (Note 2).
 
Add additional immunosuppressive agents in severe refractory cases.
 
	✓

Property of the Sanofi Group - strictly confidential

PAGE 72 OF 217

## Amended Clinical Trial Protocol 07

KY1044/SAR445256-KY1044-CT01/TCD17370 - alomfilimab

10-Nov-2021 Version number: 1

		• Give additional supportive treatments, including appropriate treatment of heart failure. Additional treatment of detected cardiac conditions should be provided.*		

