#### 9.4.3 Safety Analysis

The Phase 1 primary and Phase 2 secondary safety endpoints include:

- Safety: Incidence and severity of AEs and SAEs, including changes in laboratory parameters, vital signs and ECGs
- Tolerability: Dose interruptions, reductions and dose intensity

For Phase 1, the primary endpoints will also include:

- The incidence of DLTs with KY1044 as single agent during the first 21 days of treatment
- The incidence of DLTs with KY1044 in combination with atezolizumab during the first 21 days of treatment

All AEs in the clinical trial database will be coded according to the Medical Dictionary for Regulatory Activities (MedDRA) Version 21.0 or higher, which will be used to summarize AEs by primary system organ class (SOC) and preferred term (PT). All AEs will be displayed in listings.

A treatment emergent adverse event (TEAE) is defined as an AE observed after starting administration of the specific treatment. If a patient experiences an event both prior to and after starting administration of a treatment, the event will be considered a TEAE (of the treatment) only if it has worsened in severity (ie, it is reported with a new start date) after starting administration of the specific treatment, and prior to the start of another treatment, if any. All TEAEs collected during the investigational period will be summarized.

Treatment-related AEs/SAEs coded by primary SOC and PT will be summarized in those receiving at least one infusion of KY1044.

Additional summaries by severity of AEs/SAEs will also be produced.

Actual and change from baseline data for vital signs and ECG parameters will be reported using summary statistics.

When relevant, for laboratory variables, descriptive statistics for results and changes from baseline will be provided during the on-treatment period. These analyses will be performed using local measurements for laboratory variables. Clinical laboratory results will be graded according to NCI CTCAE version 5.0, when applicable. Number (%) of participants with laboratory abnormalities (all grades and by grade) using the worst grade during on-treatment period will be provided for the all-treated population.

When the NCI CTCAE version 5.0 scale is not applicable, the number of participants with laboratory abnormality out-of-normal laboratory range value will be displayed.

The number of dose interruption, reductions and incidence of DLTs will be summarized.

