10.5.2 Primary Endpoint

Phase 1

- Safety: Incidence and severity of AEs and SAEs, including changes in laboratory parameters, vital signs and ECGs.
- Tolerability: Dose interruptions, reductions and dose intensity
- The incidence of DLTs with KY1044 as single agent during the first 21 days of treatment
- The incidence of DLTs with KY1044 in combination with atezolizumab during the first 21 days of treatment

Phase 2

• ORR per RECIST 1.1.

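### The protocol promises summaries of ECG parameters for its safety endpoints, but SAP 10.7.5.2 summarises QTcF alone, so other collected ECG parameters have no by-visit or change-from-baseline summary

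*SAP*

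**What the plan says.** **Protocol.** Section 2.2.1 includes changes in ECGs in the Phase 1 primary safety endpoint. Section 2.2.2 makes them a secondary safety endpoint in Phase 2. The analysis is stated twice. Section 9.4.3: "Actual and change from baseline data for vital signs and ECG parameters will be reported using summary statistics". The synopsis, under the Phase 1 primary endpoints: "Actual and change from baseline data for vital signs, ECG parameters and clinical laboratory values will be reported using summary statistics". Neither place limits ECG parameters to QTc.

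**SAP.** Section 10.5.2 carries the endpoint over unchanged: "Safety: Incidence and severity of AEs and SAEs, including changes in laboratory parameters, vital signs and ECGs". The ECG analysis itself is in section 10.7.5.2:
- By-visit summary: "The mean QTcF (msec) from ECGs performed in triplicate periodically over the study period will be summarized at scheduled time points/visits".
- Change from baseline: "Change in QTcF from baseline at all scheduled post-baseline time points/visits will also be summarized".
- A listing over time, of QTcF.
- A count and percentage of patients with ECG abnormalities, introduced by "Abnormality criteria to be used in the determination of ECG abnormalities are defined as follows". The only parameter in the table that follows is QTcF.
- A listing of all ECG parameter values, restricted to patients who meet one of those criteria.
- A by-patient listing of post-dose abnormal findings as judged by the investigator or cardiologist, for each type of abnormality.

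The SAP gives no reason for narrowing the protocol's analysis, and its Document History records no such change.

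**The concern.** The SAP delivers less than the protocol commits to for a component of the Phase 1 primary endpoint, and does not say so. The protocol itself treats other ECG findings as relevant: the cardiac part of Table 5-5 names "QTc prolongation, new conduction disease, or ST-T wave changes" together as new ECG findings. Section 6.5.8 schedules triplicate ECGs before infusion and 1.5 hours after its start in Cycles 1, 3 and 6, timed to the PK samples. Data that could show a dose-related shift in a conduction interval may therefore already be collected in a first-in-human study, yet no planned table would show the shift.

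There is also a labelling problem. A table presented as the count of patients with ECG abnormalities, but built only from QTcF thresholds, invites the reader to take a zero as meaning no abnormal ECGs.

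**Working it through.** No arithmetic beyond counting applies. The check compares the protocol's commitment with each planned ECG output and then follows a non-QTcF finding through all the SAP's safety outputs.

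**Step 1: outputs in SAP 10.7.5.2.** The criteria table has three bands for the maximum post-baseline value (450 to <480, 480 to <500, and ≥500 msec) and two for the maximum change (30 to <60 and ≥60 msec), so 3 + 2 = 5 categories.

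| Output | Parameters covered |
|---|---|
| By-visit values | QTcF |
| By-visit change from baseline | QTcF |
| Listing over time | QTcF |
| Patients with abnormalities, 5 categories | QTcF in all 5 |
| Listing of every ECG parameter value | All, but only for patients meeting a QTcF criterion |
| Listing of assessed abnormal findings | Any type; listing only, no count |

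Both by-visit summaries and all five categories are QTcF only. The fifth row also shows that the SAP expects parameters other than QTcF to be recorded.

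**Step 2: other safety outputs.**
- Protocol 6.5.8 requires an ECG abnormality judged clinically significant to be recorded as an AE. It then enters the TEAE tables in SAP 10.7.1, by SOC, PT, maximum CTCAE grade and relatedness.
- SAP 10.7.4 summarises vital signs by visit with change from baseline, and counts heart rate <60 or >100 beats/min as abnormal. That covers rate as a vital sign, not ECG-derived rate or any conduction interval.

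**Step 3: trace a patient.** Take a patient whose QTcF stays below 450 msec with a change below 30 msec, and whose conduction interval changes on treatment. The contribution to the five categories is 0 in each case below.

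| Judgement of the finding | Where it appears |
|---|---|
| Abnormal and clinically significant | TEAE tables, and the listing of assessed findings |
| Abnormal, not clinically significant | Listing of assessed findings only; no count |
| Shift not judged abnormal | No planned output shows the values |

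The gap is the second and third rows. A mean shift across dose levels, made up of changes each within what an investigator would call normal, belongs to the third row. That is what the summaries promised in protocol 9.4.3 would show.

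**The case against.** The strongest case against has four parts.

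1. **Findings are not lost.** A reader might infer that conduction and rate changes can appear nowhere in the report. The documents do not support that. Clinically significant findings are counted and graded as TEAEs, and AE incidence and severity are the core of the same endpoint. Heart rate is summarised and counted as a vital sign, and section 6.5.7 has it measured every 15 minutes during infusions in Cycles 1 and 2, far more often than ECGs are taken. This objection stands and limits the point to interval shifts and findings not judged clinically significant.

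2. **Cardiac risk is handled elsewhere.** It is tempting to argue that myocarditis could be missed. Appendix 3 makes Grade 2 or higher cardiac disorders AESIs for atezolizumab, and SAP 10.7.1 tabulates AESIs. The ECG table is not the planned route to those events. This also stands. Table 5-5 is toxicity-management guidance rather than an analysis specification, so it supports the relevance of non-QTc findings but creates no reporting duty.

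3. **The collected intervals are unknown.** Neither document names PR, QRS or ECG heart rate as recorded, and the ECG CRFs are not part of the documents. The fix must therefore refer to whatever those CRFs collect. New cut-offs for PR or QRS, or a listing of every parameter for every patient, would go beyond protocol 9.4.3.

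4. **The study is descriptive.** SAP 10.0 plans no formal testing, so no inference is affected. True, but the descriptive summaries are the planned analysis of the endpoint. The AE route depends on case-by-case judgement and cannot show a shift in a mean.

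**Conclusion.** The mismatch holds in a limited form. The protocol twice commits to summaries of actual values and changes for ECG parameters; the SAP provides them for QTcF alone. Any other collected ECG parameter has no by-visit summary or change from baseline, and its values are listed only for patients already flagged on QTcF. What is lost is a dose-level view of interval shifts and of abnormal findings not judged clinically significant. It is a reporting gap in a component of the Phase 1 primary and Phase 2 secondary safety endpoints. Neither clinically significant cardiac findings nor vital-sign heart rate is lost.

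The conclusion rests on two assumptions: that the criteria table in SAP 10.7.5.2 has no parameter row other than QTcF, as it reads here, and that the ECG CRFs record at least one parameter besides QTcF, as that section's own reference to all ECG parameter values implies. If QTcF were the only parameter recorded, the summaries would be complete for the data, and only the missing tabulation of assessed abnormalities and the table label would remain.

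**What to change.** In SAP 10.7.5.2:
1. Add by-visit summaries of actual values and change from baseline, using the mean of the triplicate, for every ECG parameter collected on the ECG CRFs.
2. Tabulate the number and percentage of patients with post-baseline ECG abnormalities as assessed by the investigator or cardiologist, from the data already planned as a listing. Present this by dose level in Phase 1 and by the reporting groups of SAP 10.0 in Phase 2.
3. Retitle the existing threshold table as QTcF abnormalities, so that a zero there is not read as no abnormal ECGs.

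If the sponsor prefers to keep QTcF alone, the SAP should state this as a departure from protocol 9.4.3 and give the reason.

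The cost is a few extra tables and their programming. The ECGs are already scheduled, so no new assessments are needed. The change should be made before database lock.

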12.0 Appendix

12.1 Example mTPI-2 Decision Table

Number of Patients 2 3 4 6 7 10 1 5 8 9 mTPI mTPI2 mTPI mTPI2 mTPI mTPI2 mTPI mTPI2 mTPI mTP12 mTPI mTPI2 mTPI mTPI2 mTP1 mTPI2 mTPI mTPI2 mTPI mTPI2 0 E E Ε E E E E E E E E E È E E Ē E E E E D D D s 1 s s s S E E E S E E E Ε E E E E 2 DU DU D Đ. s D s D s s 5 s s s s E s Ē Number of DLTs 3 DU DU DU DÜ D D s D s D s Ð s s s S 4 DU DU DU DU DU DU D D D D s D s D 5 DU D D 6 DU 7 DU DU DU DU DU DU DU DU 8 DU DU DU DU DU DU 9 DU DU DU DU 10 DU DU E: Escalate to the next higher dose; S: Stay at the same dose; D: De-escalate to the previous lower dose; DI: De-escalate to the previous lower dose and the current dose will never be used again in the trial;

Column indicates the number of patients treated. **Row** indicates the number of patients with DLTs. Decisions for both mTPI and mTPI-2. For each column (the number of patients treated), there are two sub-columns listing the decisions of mTPI and mTPI-2 side by side. Here, the target toxicity probability $p_T=0.30$, $e_I=0.05$ and $e_2=0.05$.

13.0 Glossary of Abbreviations

Glossary of Abbr	eviations:
ADA	Anti-drug Antibody
AE	Adverse event
AESI	Adverse Events of Special Interest
ATC	Anatomic Therapeutic Classification
AUC	Area under the Concentration-Time Curve
AUC _{0-infinity}	Area under the Concentration-Time curve from 0 to infinity
AUC _{0-last}	Area under the Concentration-Time curve from 0 to last measurable concentration
BMI	Body Mass Index
BOR	Best Overall Response
CD	Cluster of Differentiation
CFB	Change from baseline
CI	Confidence Interval
C _{max}	Minimum Concentration
Cmin	Maximum Concentration
CR	Complete Response
CRF	Case Report Form
CSR	Clinical Study Report
CTMS	Clinical Trials Management System
DMC	Data Monitoring Committee
DOR	Duration of Response
DLT	Dose Limiting Toxicity
DSMB	Data Safety Monitoring Board
ECG	Electrocardiogram
ECOG	Eastern Cooperative Oncology Group
FAS	Full Analysis Set
FOXP3	Forkhead box P3
HCC	Hepatocellular Carcinoma
HNSCC	Head and Neck Squamous Cell Carcinoma
IC	Immune Cells
iCR	immune-Confirmed Response
ICOS	Inducible T cell Costimulator

iCPD	immune-Unconfirmed Progressive Disease
IFNγ	Interferon Gamma
lgG	Immunoglobulin G
IHC	Immunohistochemistry
iPR	immune-Partial Response
irAEs	Immune-related Adverse Events
IRECIST	immune- Response Evaluation Criteria in Solid Tumors
iSD	immune-Stable Disease
iUPD	immune-Unconfirmed Progressive Disease
i.v	Intravenous
IVRS	Interactive Voice Response System
MedDRA	Medical Dictionary for Regulatory Activities
mRNA	Messenger Ribonucleic Acid
MTD	Maximal Tolerated Dose
mTPI-2	Modified Toxicity Probability Interval Design No 2
NCA	Non- Compartmental Analysis
NE	Not Evaluable
NSCLC	Non-Small Cell Lung Cancer
ORR	Objective Response Rate
OS	Overall Survival
PBMCs	Plasma and peripheral blood mononuclear cells
PD	Pharmacodynamics
PD-1	Programmed Cell Death Protein-1
PD-L1	Programmed Cell Death-Ligand 1
PFS	Progression Free Survival
PK	Pharmacokinetic
PP	Per Protocol
PR	Partial Response
PT	Preferred Term
Q3W	Every 3 Weeks
R2PD	Recommended Phase 2 Dose
RECIST 1.1	Response Evaluation Criteria in Solid Tumors Version 1.1
RNA	Ribonucleic Acid
RO	Receptor Occupancy

SAP	Statistical Analysis Plan
SAE	Serious Adverse Event
SD	Stable Disease
SOC	System Organ Class
STD	Standard Deviation
t1/2	Half-life
t _{max}	Time to maximum observed serum concentration
TEAE	Treatment Emergent Adverse Events
TCR	T Cell Receptor
TILs	Tumor-Infiltrating Lymphocytes
TNFα	Tumor Necrosis Factor alpha
WHO	World Health Organization

15.0 Document History

Version/Date	Change Log
1.0/08-Nov-2019	Created as new
2.0/17-Aug-2021	As the new template of SAP is used. Hence, the section number and corresponding section description is updated.
	Sections updated as per Protocol Version 6.0.

F1010C01 NO. K 11044-C101		
	Additional approvers from Kymab are added in.	
	• In the entire document the text "Estimands" is replaced with "Endpoints".	
	 In the entire document the text "Overall Response Rate" is replaced with "Objective Response Rate". 	
	Section 8.0 Study Design	
	• The treatment duration is updated to 48 months as per protocol amendment version 6.0.	
	The figure of study design is added.	
	• Enrollment for patients in Phase 1 and Phase 2 is detailed as in protocol.	
	Section 9.2 Analysis Sets	
	 The screened subject and enrolled subject are defined separately. 	
	Section10.3 Prior and Concomitant Medications	
	The medication taken post-study are defined.	
	• The medication that can be flagged as "Prior and Concomitant" are defined.	
	 Section 10.4 End of Study for Individual Patient is included. 	
	The definition of Time since Initial Diagnosis is included in Section 10.5.	
	Section 10.6 Efficacy Analysis	
	 The derivation of Duration of Response and Progression-free Survival by iRECIST is included. 	
	 The confirmatory Stable Disease response criteria is considered of 7 weeks. 	
	Section 10.8.2 Treatment Emergent Adverse Events	
	 The below text in the definition "Plus 21 days" is rephrased as "up to 21 days after the last dose". 	
	Section 12.0 Statistical Analysis Method	
	 The tables, figures and listings for the Phase II part of the study will be presented by indication and dose group(s) within KY1044 single agent and KY1044 combination groups, split by anti-PD-(L)1 naïve and pre-treated groups. 	
	Section 12.4 Protocol Deviations	
	 The listing of protocol deviation for all deviations related to COVID-19 is included. 	
	Section 12.5 Efficacy Analyses	
	 In this section the endpoints and analysis is separated by primary, secondary and exploratory endpoints. 	
	 The confidence interval of median, 25th and 75th percentile of progression- free survival and overall survival is updated to use Brookmeyer-Crowley method. 	
	 The confidence interval for 12 and 24 months' survival rates of progression- free survival and overall survival is updated to use complementary log-log transformation method. 	
	Section 12.7 Safety Analysis	
	 The definition of treatment emergent adverse is updated to match the protocol. 	
	• The definitions of adverse events, dose limiting toxicity are removed as they are not need for the analysis.	
	Section 13 Reference	
	 The references for Bayesian interval dose-finding design and Modified Toxicity Probability Interval Design is added in. 	

	Section 14 Appendix
	 The example of mTPI-2 decision table is included.
	Section 15 Glossary of Abbreviations
	 The list abbreviation is updated to include all abbreviations used in this document.
3.0/xx-Mar-2024	Update the definition of safety analysis set in section 7.2.4
	Update the definition of BOR in section 8.6.1
	Update the PK section 10.6.1
	Update the SAP template per IOD harmonized processes
